### **3.2.3 Nivolumab Clinical Activity**

Nivolumab has demonstrated durable responses exceeding 6 months as monotherapy in several tumor types, including NSCLC, melanoma, RCC, classical Hodgkin's lymphoma (cHL), SCLC, gastric cancer, SCCHN, urothelial cancer, HCC, and colorectal cancer (CRC). In confirmatory trials, nivolumab as monotherapy demonstrated a statistically significant improvement in OS as compared with the current standard of care in patients with advanced or metastatic NSCLC, unresectable or metastatic melanoma, advanced RCC, or recurrent or metastatic SCCHN. Details of the clinical activity in these various malignancies are provided in the USPI and SmPC.

### **3.2.4 Relatlimab Mechanism of Action**

Relatlimab is a fully human antibody specific for human LAG-3 that was isolated from immunized transgenic mice expressing human Ig genes. It is expressed as an IgG4 isotype antibody that includes a stabilizing hinge mutation (S228P) for attenuated Fc receptor binding in order to reduce or eliminate the possibility of antibody- or complement-mediated target cell killing. Relatlimab binds to a defined epitope on LAG-3 with high affinity

### **3.2.5 Nivolumab Mechanism of Action**

Nivolumab (also referred to as BMS-936558, MDX1106, or ONO-4538) is a human monoclonal antibody (HuMAb; immunoglobulin G4 [IgG4]-S228P) that targets the PD-1 CD279 cell surface membrane receptor. PD-1 is a negative regulatory molecule expressed by activated T and B lymphocytes. Binding of PD-1 to its ligands, PD-L1 and PD-L2, results in the down-regulation of lymphocyte activation. Inhibition of the interaction between PD-1 and its ligands promotes immune responses and antigen-specific T-cell responses to both foreign antigens as well as self-antigens. Nivolumab is expressed in Chinese hamster ovary (CHO) cells and is produced using standard mammalian cell cultivation and chromatographic purification technologies. The clinical study product is a sterile solution for parenteral administration.

Nivolumab (OPDIVOTM) is approved for the treatment of several types of cancer in multiple regions including the United States (US, Dec-2014), the European Union (EU, Jun-2015), and Japan (Jul-2014).

### **3.2.6 Nivolumab Combined with Relatlimab Clinical Safety**

The Phase 1/2a study CA224020 enrolled the highest number of participants treated with the combination therapy of nivolumab + relatlimab in dose-escalation (Part B) and expansion cohorts in Parts C, D, [REDACTED] tested in every 2 week (Q2W) and Q4W dosing intervals.

[REDACTED] Part C included expansion cohorts with multiple tumor types and Parts D [REDACTED] included advanced melanoma participants (1L and progressed on prior-PD-1 therapy). [REDACTED]

Troponin is a highly sensitive non-specific indicator of myocardial injury. Troponin is not typically monitored during treatment with immune checkpoint inhibitors due to uncertain value in preventing immune-related cardiac morbidity.

While myocarditis is a recognized risk with immune checkpoint inhibitors, routine troponin monitoring during treatment has not been recommended by clinical guidelines due to lack of demonstrated value in preventing morbidity or mortality.

The safety profile of the combination of nivolumab 480 mg + relatlimab 160 mg FDC Q4W was confirmed in the pivotal Phase 2/3 global, multicenter study CA224047 (n = 355), in previously untreated advanced melanoma participants (clinical data cutoff 09-Mar-2021). The study findings demonstrated a well-tolerated regimen with a manageable safety profile and without unexpected safety signals. The incidence of Grade 3-4 drug-related AEs was 18.9% in the nivolumab + relatlimab FDC group versus 9.7% in the nivolumab monotherapy group. There were 3 treatment-related deaths with nivolumab + relatlimab FDC and 2 with nivolumab monotherapy. Drug-related AEs (any grade) led to treatment discontinuation in 14.6% and 6.7% of patients in the nivolumab + relatlimab FDC and nivolumab monotherapy groups, respectively. Refer to relatlimab + nivolumab FDC IB Section 5.5.2 for an updated safety analysis based on the clinical data cutoff date of 30-Jun-2021.

### 3.3 Benefit/Risk Assessment

As described in [Section 3.2.2](#), clinical activity was seen with the combination of nivolumab + relatlimab in multiple tumor types, including treatment naive and previously heavily treated tumors including previous anti-PD-1 therapy, in the CA224020 study. The clinical efficacy of the combination was further confirmed in study CA224047, a global, double-blind Phase 2/3 randomized controlled trial that demonstrated a statistically significant and clinically meaningful PFS benefit of nivolumab + relatlimab FDC Q4W compared to nivolumab 480 mg Q4W, as well as clinically meaningful improvement in OS and ORR, although the OS result was not statistically significant and ORR could not be formally tested.

The combination of nivolumab and relatlimab has shown well-defined toxicity profiles based on a safety database comprised of participants treated with either relatlimab monotherapy or as a combination across multiple tumor types. [REDACTED]

[REDACTED] The most frequent drug-related AEs included fatigue, decreased appetite, pruritus, diarrhea, rash, rash maculo-papular, anemia, arthralgia, increased lipase, nausea, dry mouth, asthenia, hypothyroidism, hyperthyroidism, cough, pyrexia, increased alanine aminotransferase, and increased aspartate aminotransferase. Immune-mediated AEs (IMAEs) seen with nivolumab in combination with relatlimab appear consistent with those seen with other immunotherapy agents, and can potentially include pneumonitis, colitis, hepatitis, nephritis, endocrinopathy, neurologic, and skin AEs. In combination with nivolumab, the frequency, severity, and reversibility of IMAEs appear consistent with the mechanisms of action of either drug. The majority of all drug-related AEs and IMAEs were reversible or manageable by withholding study intervention administration, providing standard medical care, and/or following IMAE management algorithms (see [Appendix 5](#)). Most immune-mediated study intervention-related endocrinopathies will require life-long management by hormone replacement therapies. The overall safety profile of nivolumab + relatlimab across these studies remains unchanged and manageable with established management guidelines (including myocarditis cases). [REDACTED]

Furthermore, nivolumab 480 mg + relatlimab 160 mg FDC (3:1) administered Q4W was confirmed to be well tolerated with a manageable safety profile in 355 1L advanced melanoma participants treated in the CA224047 study. There were no unexpected safety signals from this combination. [REDACTED]

Safety results to date indicate that sequential, co-administration, and the FDC of nivolumab + relatlimab administration have similar manageable safety profiles that are consistent with the

mechanisms of action of each agent, nivolumab and relatlimab. No new types of clinically important events have been identified.

Given the safety profile of relatlimab as monotherapy and combination therapy observed to-date, and the positive benefit-risk of the pivotal Phase 2/3 study of nivo + rela FDC (3:1) demonstrated in participants with previously untreated metastatic or unresectable advanced melanoma, and the significant unmet medical need in adjuvant treatment for Stage III-IV resectable melanoma population, the continuing evaluation of nivo + rela FDC is justified for the patient population in this protocol.

Investigators and the Sponsor will utilize continuous safety assessments to determine whether additional safety measures or termination from the study is required at any time. In addition, AEs and SAEs will be reviewed on an ongoing basis by the Sponsor's Medical Monitor/designee and Worldwide Patient Safety (WS) representatives to monitor for any safety signals or trends. As relatlimab is an experimental agent, it is possible that unforeseen, unknown, or unanticipated reactions may occur; however, data shows that nivo + rela is safe and tolerable at 480 mg nivolumab + 160 mg relatlimab Q4W using FDC product in other studies.

**3.3.1 Risk Assessment****Table 3.3.1-1: Risk Assessment**

Potential Risk of Clinical Significance	Summary of Data/Rationale for Risk	Mitigation Strategy
Study Interventions		
Immune-mediated AEs (eg, colitis, diarrhea/colitis, pneumonitis, hepatitis, nephritis, endocrinopathy, rash, neurologic, AEs)	FDC (BMS-986213) IB	Recommended IMAE management algorithms are included in Appendix 5 or as per institutional protocol/investigator discretion
Potential Infusion Related Reaction	FDC (BMS-986213) IB	Recommended management algorithms are included in Appendix 5 or as per institutional protocol/ investigator discretion
Dermatologic AEs	Nivolumab IB	Recommended management algorithms are included Appendix 5 or as per institutional protocol/ investigator discretion
Cardiovascular AEs (ie, myocarditis, troponin elevation)	FDC (BMS-986213) IB	Management of Myocarditis per AE Management Algorithm in Appendix 5 or as per institutional protocol/ investigator discretion.
Hemorrhage AE (eg, epistaxis, gingival bleeding, GI blood loss)	Relatlimab IB	Monitor clinical signs/symptoms/ CBC and coagulation parameters. Management as per institutional protocol/investigator
Opportunistic Infections due to Immunosuppression	FDC (BMS-986213) IB	Monitor signs/symptoms, may require additional laboratory tests. Management as per institutional protocol/investigator
Potential developmental toxicity	FDC (BMS-986213) IB	Exclusion criteria, pregnancy testing, contraception per protocol, as per Section 6.1, 4) and Appendix 4 .
Study Procedures		
Tumor Biopsy (eg, pain, infection)	Not applicable	Per institutional protocol/ investigator discretion.
Phlebotomy (eg, pain, ecchymosis, bleeding, syncope)	Not applicable	Per institutional protocol/ investigator discretion.
MRI	Not applicable	Management per institutional protocol/investigator discretion.
CT	Not applicable	Management per institutional protocol/investigator discretion.
Ultrasound	Not applicable	Management per institutional protocol/investigator discretion.

**Table 3.3.1-1: Risk Assessment**

Potential Risk of Clinical Significance	Summary of Data/Rationale for Risk	Mitigation Strategy
Other (if applicable)		
Allergy to contrast agent (eg, reaction to anaphylaxis)	Not applicable	Prophylaxis and/or treatment per institutional protocol/ investigator discretion

Abbreviations: AE, adverse event; CBC, complete blood count; CT, computed tomography; FDC, fixed dose combination; GI, gastrointestinal; IB, investigator brochure; IMAE, immune-mediated adverse events; MRI, magnetic resonance imaging.

### **3.3.2 Benefit Assessment**

This study investigates if the adjuvant use of systemic therapy of nivo + rela FDC will improve recurrence free survival (RFS) for Stage III-IV completely resected melanoma participants with no evidence of disease. Currently, nivolumab monotherapy is an approved treatment for adjuvant melanoma patients in many countries. While nivo + rela FDC provided PFS benefit for the treatment of untreated metastatic or unresectable melanoma, it is not yet approved for any indication.

Despite the availability of effective adjuvant therapies, there is an unmet need to provide safe and effective adjuvant systemic therapy that offers additional clinical benefit in RFS in this patient population. It is unknown if nivo + rela FDC will improve RFS compared to nivolumab monotherapy. Although benefits are hypothesized, actual clinical benefits to patients with Stage III or Stage IV resectable melanoma have not been established yet. Participation in this study may help offer new therapies for advanced resectable melanoma patients and establish the clinical benefits of the combination therapy.

Participants enrolled in this study will be randomized to either the nivo + rela FDC or nivolumab monotherapy. Participants will have an equal chance of being randomized to the nivo + rela FDC therapy or the standard of care nivolumab monotherapy.

### **3.3.3 Overall Benefit/Risk Conclusion**

Taking into account the measures taken to minimize risk to participants in this study, the potential risks identified in association with nivo + rela FDC are justified by the anticipated benefits that may be afforded to participants with resectable melanoma.

The Sponsor will evaluate the risk/benefit profile of the study on an ongoing basis. This evaluation will be based on all available data – with particular attention to: (i) AEs or other safety trends in this or any other clinical study of nivo + rela FDC whose character, severity, and/or frequency suggest that participants would be exposed to an unreasonable and significant risk of illness or injury; (ii) new nonclinical data suggesting unreasonable and significant risk of illness or injury.

If such evaluation suggests that the risk/benefit profile of the study has become unfavorable to participants, the Sponsor will pause enrollment and/or treatment until further evaluation of data,

and interaction with the appropriate Health Authority(ies) can take place on potential actions. Such actions may include (but are not limited to) study continuation, substantial amendment, or termination of the study.

## 4 OBJECTIVES AND ENDPOINTS

**Table 4-1: Objectives and Endpoints**

Objectives	Endpoints
Primary	

To compare the efficacy, as measured by RFS, provided by nivo + rela FDC vs nivolumab monotherapy in participants with completely resected Stage III/IV NED melanoma.

	

RFS time as assessed by the investigator. RFS is defined as the time between the date of randomization and the first date of documented recurrence [REDACTED] or death due to any cause, whichever occurs first.

Key Secondary	

To compare the OS provided by nivo + rela FDC vs nivolumab monotherapy in participants with completely resected Stage III/IV NED melanoma.

	

OS is defined as the time between the date of randomization and the date of death due to any cause.

Other Secondary	

To assess the efficacy, as measured by DMFS, provided by nivo + rela FDC vs nivolumab monotherapy in participants with completely resected Stage III/IVA/IVB NED melanoma.

To assess safety and toxicity of nivo + rela FDC vs nivolumab monotherapy in participants with completely resected Stage III/IV NED melanoma.

To evaluate investigator-assessed outcomes on next-line systemic therapies.

	

DMFS, by investigator, is defined as the time between the date of randomization and the date of first distant metastasis or date of death due to any cause, whichever occurs first.

Incidence and severity of AE, SAEs, AEs leading to DC, IMAEs, drug-related AEs, deaths, laboratory abnormalities, and other select AEs.

PFS2 defined as time from randomization to second recurrence/objective disease progression on next-line systemic therapy per investigator, or death from any cause, whichever occurs first.

Exploratory	

**Table 4-1: Objectives and Endpoints**

Objectives	Endpoints

Abbreviations: AE(s), adverse event(s); DC, discontinuation; DMFS, distant metastasis-free survival; FDC, fixed dose combination; NED, no evidence of disease; nivo, nivolumab; PFS2, progression-free survival 2; RFS, recurrence-free survival; OS, overall survival; rela, relatlimab; SAE, serious adverse event;

a

## 5 STUDY DESIGN

### 5.1 Overall Design

This is a Phase 3, randomized, double-blind study of nivo + rela FDC compared with nivolumab monotherapy in participants ( $\geq 12$  years of age) with completely resected Stage IIIA ( $> 1$  mm tumor in lymph node)/B/C/D or Stage IV NED melanoma by American Joint Committee on Cancer version 8 (AJCC v8). Efficacy of nivo + rela FDC, as measured by RFS time (as assessed by the investigator), will be compared to nivolumab monotherapy.

Participants will be randomized 1:1 to receive treatment with one of the following:

[figure not shown]
- Nivo + rela FDC dosing:
  - $\geq 18$  years of age **OR**  $\geq 12$  years to  $< 18$  years of age and  $\geq 40$  kg: nivolumab 480 mg and relatlimab 160 mg IV every 4 weeks (Q4W)
  - $\geq 12$  years to  $< 18$  years of age and  $< 40$  kg: [REDACTED]
- Nivolumab dosing:
  - $\geq 18$  years of age **OR**  $\geq 12$  years to  $< 18$  years of age and  $\geq 40$  kg: nivolumab 480 mg IV Q4W
  - $\geq 12$  years to  $< 18$  years of age and  $< 40$  kg: nivolumab 6 mg/kg IV Q4W

Participants will be stratified by AJCC v8 stage ([Appendix 7](#)) and geographic region. All participants will be treated until: recurrence of disease [REDACTED]  
[REDACTED], unacceptable toxicity, participant withdrawal of consent, or a maximum of 1 year of treatment from first dose (maximum of 13 doses), whichever occurs first.

This study will consist of 3 phases: screening, treatment, and follow-up. For a complete list of study required procedures, please refer to [Section 2](#).

The study design schematic is presented in [Figure 5.1-1](#).

### Figure 5.1-1: Study Design Schema

Abbreviations: AJCC v8, American Joint Committee on Cancer version 8; ECOG, Eastern Cooperative Oncology Group; FDC, fixed dose combination; [REDACTED] IV, intravenous; LN, lymph node; NED, no evidence of disease; ROW, rest of the world; Q4W, every 4 weeks

a Stratification:

- AJCC v8: Stages IIIA/IIIB, Stage IIIC, Stages IIID/IV (including all participants with mucosal melanoma, Stage III, Stage IVA, Stage IVB, and Stage IVC)
- Geographic Regions: USA/Canada/Australia, Europe, ROW

b Nivo + rela FDC dosing:

- $\geq 18$  years of age **OR**  $\geq 12$  years to  $< 18$  years of age and  $\geq 40$  kg: nivolumab 480 mg and relatlimab 160 mg IV Q4W.
- $\geq 12$  years to  $< 18$  years of age and  $< 40$  kg: [REDACTED]

[figure not shown]
c Nivolumab dosing:

- $\geq 18$  years of age **OR**  $\geq 12$  years to  $< 18$  years of age and  $\geq 40$  kg: nivolumab 480 mg IV Q4W.
- $\geq 12$  years to  $< 18$  years of age and  $< 40$  kg: nivolumab 6 mg/kg IV Q4W.

### **5.1.1 Data Monitoring Committee and Other Committees**

When required, adjudicated events will be submitted to the Data Monitoring Committee (DMC) and Health Authorities for review on a specified timeframe in accordance with the adjudication documentation.

A DMC will be established to provide oversight of safety and efficacy considerations and to provide advice to the Sponsor regarding actions the committee deems necessary for the continued protection of participants enrolled in the study. The DMC will be charged with assessing such actions in light of an acceptable benefit/risk profile for nivo + rela FDC. The DMC will act in an advisory capacity to BMS and will monitor participant safety and evaluate the available efficacy data for the study. The oncology therapeutic area of BMS has primary responsibility for design and conduct of the study.

Details of the DMC responsibilities and procedures will be outlined in the DMC charter.

A Study Steering Committee (SSC), consisting of Investigators and personnel members representing the Sponsor of the study, will be established to obtain scientific guidance and advice for the protocol and conduct of the study. Details of the SSC responsibilities and procedures will be specified in the SSC charter.

### **5.2 Number of Participants**

Approximately 1,050 participants are expected to be randomized to the following treatment arms:

- Nivo + rela FDC (n = 525)
- Nivolumab monotherapy (n = 525)

See [Section 10.2](#) for sample size determination.

The randomization will be stratified by the following stratification factors:

- Geographic region (USA/Canada/Australia vs Europe vs ROW)
- American Joint Committee on Cancer (AJCC v8) Stage IIIA/IIIB vs Stage IIIC vs Stage IIID/IV (including all participants with mucosal melanoma, Stage III, Stage IVA, Stage IVB, and Stage IVC - see [Appendix 8](#))

### **5.3 End of Study Definition**

The start of the trial is defined as the first participant screened. End of trial is defined as the last visit or scheduled procedure shown in the Schedule of Activities for the last participant.

Study completion is defined as the final date on which data for the primary endpoint was or is expected to be collected, if this is not the same.

A participant is considered to have completed the study if he/she has died, is lost to follow-up, has withdrawn consent, the study has concluded, the last visit completed, or has been [REDACTED]

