**Brief Summary:**

The purpose of this study is to assess the efficacy, measured as RFS, of nivo + rela FDC compared with nivolumab monotherapy, in the setting of adjuvant treatment of Stage III-IV melanoma after complete resection. Study details are as follows.

Study drug will be given for a maximum of 1 year from first dose (maximum of 13 doses), [REDACTED]

While study drug is being administered, study visits will be every 4 weeks (for a maximum of 1 year). Once study intervention is completed or discontinued early, the first follow-up visit will be 30 days from the date of the last dose. The second follow-up visit is 135 days following last dose of study intervention. Long-term follow up visits will be every 12 weeks subsequently (in clinic or by telephone) [REDACTED]

[REDACTED] The trial will end once this follow-up has concluded. [REDACTED]

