### **8.2.1 Individual Discontinuation Criteria**

- A participant may withdraw completely from the study at any time at his/her own request, or may be withdrawn at any time at the discretion of the investigator for safety, behavioral, compliance, or administrative reasons. This is expected to be uncommon. Stopping study intervention is not considered withdrawal from the study.
- Site should document if subject is unwilling to attend future visits, accept phone calls, allow contact with their personal physician, or allow review of medical records for health status information.

- At the time of discontinuing from the study, an immediate follow-up visit may be needed. See the Schedule of Activities ([Section 2](#)) for data to be collected at the time of study discontinuation and follow-up and for any further evaluations that need to be completed.
- The participant will be permanently discontinued both from the study intervention and from the study at that time.
- If the participant withdraws consent for disclosure of future information, the Sponsor may retain and continue to use any data collected before such a withdrawal of consent.

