## **STUDY AND SITE START AND CLOSURE**

The Sponsor/designee reserves the right to close the study site or to terminate the study at any time for any reason at the sole discretion of the Sponsor. Study sites will be closed upon study completion. A study site is considered closed when all required documents and study supplies have been collected and a study-site closure visit has been performed.

The investigator may initiate study-site closure at any time, provided there is reasonable cause and sufficient notice is given in advance of the intended termination.

Reasons for the early closure of a study site by the Sponsor or investigator may include, but are not limited to:

- Failure of the investigator to comply with the protocol, the requirements of the IRB/IEC or local Health Authorities, the Sponsor's procedures, or GCP guidelines
- Inadequate recruitment of participants by the investigator

- Discontinuation of further study intervention development

If the study is prematurely terminated or suspended, the Sponsor shall promptly inform the investigators, the IECs/IRBs, the regulatory authorities, and any contract research organization(s) used in the study of the reason for termination or suspension, as specified by the applicable regulatory requirements. The investigator shall promptly inform the participant and should assure appropriate participant therapy and/or follow-up.

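### Do the completion definitions in Section 5.3 stop survival follow-up early or hide dropout?

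*Combined protocol and SAP*

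**What the plan says.** Section 5.3 uses two trial-level terms. The first is the end of the trial: "End of trial is defined as the last visit or scheduled procedure shown in the Schedule of Activities for the last participant". The second is study completion: "Study completion is defined as the final date on which data for the primary endpoint was or is expected to be collected". A short closing clause allows that the second date may differ from the first.

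Appendix 2, under Study and Site Start and Closure, uses the second term: "Study sites will be closed upon study completion".

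The Brief Summary in the Protocol Summary describes long-term follow-up every 12 weeks, with its length redacted, and then says: "The trial will end once this follow-up has concluded".

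On individual participants, Section 5.3 says: "A participant is considered to have completed the study if he/she has died, is lost to follow-up, has withdrawn consent, the study has concluded". The list goes on and ends in a redaction. Section 8.2.1 says: "A participant may withdraw completely from the study at any time at his/her own request". It goes on to class such a participant as permanently discontinued from both treatment and study.

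RFS by investigator is the primary endpoint and OS is the only key secondary endpoint (Table 4-1). OS has its own null hypothesis in Section 10.1.

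**The concern.** Put the Section 5.3 definition beside the Appendix 2 sentence and a literal reader gets a chain: RFS collection ends, the study is therefore complete, so sites close. OS deaths accrue more slowly than RFS events, so closing sites at that point would stop survival contacts while the key secondary test was still short of events. The protocol itself notes, in Section 5.4.4, that OS needs longer follow-up.

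The participant-level wording raises a separate worry. If death, loss, withdrawal, study conclusion and a last visit all count as completion, nearly everyone completes by definition. A single completion rate would then say nothing about how much RFS or OS information is missing, or whether it is missing unevenly between arms.

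**Working it through.** **What governs survival follow-up.** The relevant places are:

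- Section 5.3 ends the trial at the last item in the Schedule of Activities for the last participant.
- Table 2-3 puts survival status in that schedule, every 12 weeks (± 14 days) in long-term follow-up, until death, loss, withdrawal or the study's conclusion.
- Section 8.1.2 requires those who stop treatment to be followed for outcome and survival, in this study or a rollover study, until death or the study's conclusion. It also allows survival sweeps outside the scheduled windows.
- Section 10.4.1 has OS followed every 12 weeks once study drug stops.
- The Brief Summary ends the trial only after long-term follow-up.

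Against these stands one general governance sentence in Appendix 2.

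**Whether RFS collection ends early.** RFS counts death from any cause. Imaging continues every 26 weeks beyond Week 108 (Tables 2-2 and 2-3, Section 9.1.1), and no calendar stop is visible. The last date for RFS data may therefore be late, and the documents give no date from which a gap to OS could be measured.

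**The power illustration.** The plan's own OS effect, event target and alpha are not visible, so there is no stated figure to reproduce. The inputs are:

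- 525 per arm (Section 5.2).
- Control 3-year OS, S, of 77% to 86%, the two figures in Table 3.2-1. They appear to belong to the placebo and dabrafenib/trametinib arms of another trial.
- HR 0.80, the OS result of the advanced-disease study (Section 3.2.2), with HR 0.70 as an alternative.
- Exponential survival, no dropout, everyone followed for t years, two-sided alpha 0.05. All of these are assumptions.

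Deaths: d = 525 × [(1 − S^(t/3)) + (1 − S^(HR·t/3))]. Power = Φ(√(d/4) × |ln HR| − 1.96).

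For S = 0.77, HR 0.80 and t = 3: d = 525 × (0.230 + 0.189) ≈ 220, and power = Φ(7.42 × 0.223 − 1.96) = Φ(−0.31) ≈ 38%.

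| HR | Years | Deaths | Power |
|---|---|---|---|
| 0.80 | 3 | 133–220 | 25–38% |
| 0.80 | 5 | 212–340 | 37–54% |
| 0.80 | 7 | 285–442 | 47–65% |
| 0.70 | 3 | 126–209 | 52–73% |
| 0.70 | 5 | 201–323 | 72–89% |
| 0.70 | 7 | 270–422 | 83–96% |

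Events for 80% power = 4 × (1.96 + 0.8416)² / (ln HR)², which is 631 at HR 0.80 and 247 at HR 0.70.

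Longer follow-up plainly buys OS information. But at HR 0.80 the 631 events are not reached at 7 years either. That shortfall reflects the borrowed hazard ratio and the sample size, and it does not measure any effect of site closure.

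**The completer label.** Section 10.3 makes all randomized participants the analysis set for both RFS and OS, whatever a participant's completion status. Section 8.2 has withdrawal explained in the medical records and entered on the eCRF. Section 8.3 defines loss to follow-up and requires the last known alive date to be reported. Section 10.4 promises a description of disposition in the clinical study report. Nothing visible merges these categories into one completion rate.

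**The case for a change.** The best opposing case is that the longer-follow-up passages do not fully settle the matter. Table 2-3 and Section 8.1.2 run follow-up to the study's conclusion, a term the visible text does not define, and Section 8.1.2 points back to Section 5.3, where the ambiguity sits. Section 10.4.1 gives a contact interval but no visible stop date. Section 5.3 itself allows its two dates to differ, and Appendix 2 picks the one tied to RFS. On completers, the same participant is a completer in Section 5.3 and a discontinuation in Section 8.2.1. The redacted end of the list could only add further routes to completion.

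This stands as a criticism of drafting. Three end-of-study terms are not aligned, and the completer list sits awkwardly with Section 8.2.1. It does not show that survival data would be lost. A team running this trial has an explicit end-of-trial definition, a survival schedule and a key secondary OS hypothesis, and would not close sites on the strength of the Appendix 2 sentence while scheduled contacts were outstanding. The length of follow-up is redacted from the public version, so its absence cannot count against the plan. On completers, the eCRF entries for withdrawal and the reporting of loss let an analyst tabulate both by arm whatever label Section 5.3 uses.

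**Conclusion.** This is a clerical mismatch of terms, and no change to the plan follows. The end-of-trial definition and the survival follow-up requirements show that OS follow-up is meant to outlast RFS analysis if the two dates differ. The Appendix 2 sentence is naturally read in that light. The completer wording alters no analysis set: RFS and OS are analysed in all randomized participants, planned at about 1,050, under either label.

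The size of the effect on the plan's results is nil on the visible text. The 25% to 38% power figure is correct arithmetic, but it depends on a 3-year stop that the documents do not state and on effect and survival inputs that are not the plan's own. The conclusion assumes that sites follow the Schedule of Activities to its end, and that disposition is reported from the separately recorded reasons. The protocol provides for the first, and the data it collects allow the second.
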